#### 8.3. Inclusion Criteria

- 1. Children subjects 2-12 years of age at the time of the procedure, inclusive
- 2. Scheduled to undergo tonsillectomy
- 3. The Subject and Subject's Legally Authorized Representative (LAR) is willing to participate and consents to participate, as documented by signed informed consent form and/ or assent form (as applicable)

#### 8.4. Exclusion Criteria

- 1. Subjects undergoing:
  - a. Tonsillectomy as a result of cancer
  - b. Unilateral tonsillectomy
- 2. Subjects with:
  - a. Known bleeding disorders
  - b. Current peritonsillar abscess
  - c. Craniofacial disorders

MDT17024BZP

Version 5.0 (18 MAR 2019)

Page 20 of 47

Medtronic

- d. Down's syndrome (Trisomy 21)
- e. Cerebral palsy
- f. Major heart disease (including but not limited to; right-sided heart failure, left-sided heart failure, congestive heart failure, coronary artery disease, arrhythmias, chronic heart failure, acute heart failure, etc.)
- g. Current tobacco use
- 3. Subjects unable to comply with the required study follow-up visits
- 4. Female subjects pregnant at time of procedure.
- 5. The subject has comorbidities which, in the opinion of the Investigator, will not be appropriate for the study or the subject has an estimated life expectancy of less than 6 months.
- 6. The subject is participating or has participated in any drug or device research study within 30 days of enrollment.

MDT17024BZP

Version 5.0 (18 MAR 2019)

Page 21 of 47

Medtronic

#### 9. Study Procedures

#### 9.1. Schedule of Events and Study Schematic

The schematic of the study is presented in the table below.

	Screening / Baseline Day -30 to 0	Surgery (Day 0) 	Post-Op  Day 1 – Day 7, 10 & 14	Post-Op  Day 28	Return to Clinic Day 28 (+7 days)
	Can be combined		(Home)	Can b	e combined
Informed Consent 	X 				
Eligibility Criteria	X 				
Urine pregnancy test		X 			
Demographic data 	х				
Medical history	Х				
Surgical history	Х				
Medication history	Х				
Analgesic consumption & Concomitant medications (via patient diary)		Х	Х	Х	
Type of admission		Х			
Physical Examination (abbreviated)		Х			
Intra-operative bleeding volume		Х			
Tonsil measurement		Χ			
Operation time		X			
Device ease of use		Χ			
Usability Challenges 		X			
Ability to dissect tonsil via Likert scale		Х			
Alternate device used (if any)		Χ			
Post-operative bleeding		Χ	X	Χ	X
AE, SAE, ADE, USADE Assessment and device deficiencies 		Х	Х	х	Х
Readmission			Х	Х	Х
Record Pain via Wong-Baker FACES® Pain Rating Scale or FLACC behavioral pain assessment scale 			х	Х	
Patient diary			Х	Х	
Return pain scales and diary 					Х
Device accountability		Х			
Protocol deviation collection	Х	Х	Х	Х	Х

<sup>1 Study specific procedures may only be performed after subject has agreed to participate and the signed informed consent form. Screening and informed consent are considered as a process that may occur over multiple days within 30 days prior to procedure. Any new information about the subject's eligibility and willingness to participate must be considered prior to the tonsillectomy with the investigational device.

<sup>2 See protocol and CRF pages for specific data points

<sup>3 Device-related SAEs will be collected from the start of the procedure as soon as the device is in contact with the subject. If any events are ongoing at the last visit Day 28 (+7), they must be followed up to seven (7) days or resolution whichever is first

<sup>4 A negative urine pregnancy test performed within 24 hours prior to surgery will be acceptable to satisfy eligibility criteria. This will apply to all "females of child bearing potential." Local definition and standard of care for testing of "female of child bearing potential" will be documented and observed for each site.

<sup>5 For participants age 2, parents will evaluate pain using the FLACC behavioral pain assessment scale as validated measurement. All older subjects will utilize the Wong-Baker FACES Pain Rating Scale.

<sup>6 For Days 10,14, and 28, post-operative assessments including pain scales and diary may be completed +/- 1 day but should be returned Day 28 (+7).

MDT17024BZP

Version 5.0 (18 MAR 2019)

Page 22 of 47

Medtronic

#### 9.1.1. Screening / Baseline Visit

A screening/baseline visit will be performed within 30 days up to the day of the scheduled procedure and may be combined with the Procedure Visit. Subjects' legally authorized representative will need to provide consent prior any procedures specific to the study are undertaken. The purpose and all aspects of the study will be explained to the subject and LAR(s). \LAR(s) who agree to study participation must sign and personally date the sponsor and IRB/EC-approved informed consent form prior to participating in any study activities. Additionally, assent forms will be completed and signed as applicable per IRB/EC requirements.

Once informed consent/assent has been obtained according to IRB/EC requirements and eligibility is confirmed, the subject's demographics and medical history will be assessed to include: age, gender, weight, ethnicity and race. Relevant medical history will be assessed and included in the electronic case report form (eCRF).

The following assessments will be performed within 30 days prior to the scheduled surgical procedure and the results recorded on the appropriate subject eCRFs:

- Verification of eligibility criteria
- Demographic data (date of birth, ethnicity, gender height weight)
- Medical history, including comorbidities such as obesity, and underlying conditions that necessitated surgery
- Surgical history
- Medication history (such as during pre-operative period)
- Pregnancy test, if applicable (must be within 24 hours prior to surgery)
- Concomitant medication(s)
   Note: All medications will be coded using the World Health Organization (WHO) drug coding dictionary.

#### 9.1.2. Surgical Procedure (Day 0)

The Study Investigator should perform the surgical procedure according to the appropriate standard procedures and practices at his/her institution using BiZact™. BiZact™, in conjunction with other non-energy surgical tools (e.g. Allis clamp), should be used to complete the entire procedure unless it is medically necessary to use another device. Additionally, the following procedures and assessments will be performed:

- Type of admission (e.g. inpatient/outpatient)
- AE/SAE assessment
- Pre-operative procedure abbreviated physical examination
  - Including assessment of heart/lungs, neurological, ENT, immune system and vital signs (blood pressure, respiration rate, heart rate, temperature)
- Female subjects will undergo a urine pregnancy test, according to institutional and state guidelines on assessment of child-bearing potential. If the test is positive, they will be withdrawn from the study.
- Intra-operative bleeding volume (If completed within conjunction of adenoidectomy, this should be measured prior to adenoidectomy procedure)
  - Record volume of any operative field irrigant used during procedure
  - o Record presence of gastric fluids

MDT17024BZP

Version 5.0 (18 MAR 2019)

Page 23 of 47

- Record volume of fluid in suction container (i.e. stomach juices and blood) prior to stomach drainage and again after
- Differential weight of any sponges applied to the tonsil bed to absorb blood
- Surgical performance parameters
  - Operative time time from the first incision to complete hemostasis (arrest of bleeding as assessed by visual inspection of the Investigator) of the tonsillar bed (excluding closing time)
  - Device ease of use (Easy, Moderate, Difficult)
  - Ability to dissect tonsil with device graded via Likert Scale (Very Good, Good, Acceptable, Poor, Very Poor)
  - Usability Challenges (observations of the following):
    - tissue sticking
    - tissue slippage
    - accidental activation
    - visualization of tip
  - Assessment of any complications during the procedure
    - Related to bleeding
      - If there were any transfusions required and if so how much
  - Other non-investigational medical device alternative procedural devices used (if any),
    - Operation time used
    - Tonsil location (Left/Right)
    - Reason for use
  - Tonsil size measurement (volume)
- Device accountability
- Concomitant medications (including anesthesia)
   Note: All medications will be coded using the World Health Organization (WHO) drug coding dictionary.

#### 9.1.3. Post-Operative Follow-up: Days 1 through 7, Day 10, Day 14 and Day 28

Post-operative hospital stay and AE/SAE assessment will take place by delegated study personnel. Additionally, during post-operative days 1 through 7, Day 10 (+/-1 day), Day 14 (+/-1 day), and Day 28 (+/-1 day), the following assessments will be made:

MDT17024BZP

Version 5.0 (18 MAR 2019)

Page 24 of 47

Medtronic

- Pain will be assessed via the FLACC behavioral pain assessment scale (age 2) and the Wong-Baker FACES® Pain Rating Scale (Ages 3-12)
- Analgesic consumption and concomitant medications
- Ability to return to normal diet via patient diary
- Ability to return to normal activity via patient diary
- Incidence of post-operative hemorrhage any primary (≤24 hours) requiring medical intervention and secondary (>24hrs) bleeding requiring medical intervention (e.g., cautery, admission for observation, or re-operation)
- Incidence of post-operative readmission
- AE/SAE reporting

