## 8.2. Subject Enrollment

A minimum of 60 subjects will be enrolled in the study at a minimum 2 sites with competitive enrollment not to exceed 36 enrolled subjects per site. Subjects' participation in the study will last 28 (+7) days post procedure. Subjects will be considered for the study if they meet all of the preoperative inclusion criteria and none of the exclusion criteria (Section 8.3, 8.4), and sign the informed consent form.

A subject is considered enrolled in the study when the subject's legally authorized representative signs the informed consent form. However, data will not be collected for the study until the subject has determined to be eligible for the study and the surgical procedure has begun. No adverse event information will be recorded before the procedure has begun. As soon as the tonsillectomy procedure has begun and the study device has contacted the patient, the patient must be followed regardless of whether or not the procedure has been fully completed with the device . See section 9.10.3 for the full definition of enrolled subjects. The procedure will be performed per the institution's standard practice.

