## 13.4. Statistical Analysis Endpoints

### 13.4.1. Primary Endpoint

The primary hypotheses of this study are:

H0: Mean intra-operative blood loss =31 mL HA: Mean intra-operative blood loss < 31 mL

The analysis technique will be a 1-sample t-test, with a one-sided type I error rate ( $\alpha$ ) of 0.025. If intraoperative blood loss data appear to be non-normally distributed (as evidenced by p < 0.05 from a Shapiro-Wilk test), a Wilcoxon signed rank test will also be conducted.

The performance goal of 31 mL derives from a meta-analysis comparing modern technology-assisted to conventional tonsillectomy (i.e. electrocautery and cold steel) (7). This paper included a total of 3,139 patients included in thirty-three published studies. The values from the studies that reported intra-operative bleeding were combined to calculate a mean blood loss. This value encompasses a variety of techniques and technologies and a number of different studies to capture a realistic value for comparison.

Intra-operative blood loss during tonsillectomy with BiZact™ is expected to be low. The expected mean value for the BiZact™ device is a conservative estimate derived from data for LigaSure™ and other vessel sealing systems in the Alexiou meta-analysis (7). The expected standard deviation is the average of the standard deviation values for all studies that reported blood loss in the meta-analysis.

Expected mean intra-operative blood loss for BiZact™: 10 mL Expected standard deviation: 15.1 mL

Additionally, descriptive statistics for blood loss will be reported for different age groups (ages 2-5 and ages 6-12) as well as for different sites, surgeons, and countries.

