## 13.5. Statistical Analysis of Safety Endpoints

The safety endpoints will be analyzed using the ITT population. Proportions of the following events will be reported for the study:

Post-operative hemorrhage

MDT17024BZP

Version 5.0 (18 MAR 2019)

Page 39 of 47

Medtronic

- Any primary (≤24 hours) requiring medical intervention and/or secondary (>24 hours) bleeding requiring medical intervention (e.g., cautery, admission for observation, or reoperation)
- Post-operative readmission
- Evidence of glossopharyngeal nerve damage as diagnosed by the investigator via subject assessment (e.g., prolonged pain or difficulty swallowing)
- Localized Infection
  - o Infection confined to a single organ or tissue
- Other serious device-related adverse events

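### The blood-loss reading is timed to adenoidectomy, which isolates tonsillectomy blood loss only if the tonsils come out first, and the protocol does not state the order

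*Combined protocol and SAP*

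**What the plan says.** Section 9.1.2 lists intra-operative bleeding volume among the Day 0 measurements and adds: "If completed within conjunction of adenoidectomy, this should be measured prior to adenoidectomy procedure". This is the only mention of adenoidectomy in the supplied text. Combined operations are therefore expected. Section 8.3 admits any child who meets "Scheduled to undergo tonsillectomy", and section 8.4 does not exclude adenoidectomy.

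The order of the two operations is not fixed. Section 8.2 states: "The procedure will be performed per the institution's standard practice". Section 9.1.2 likewise defers to the institution's procedures.

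Two measured components feed the blood-loss figure in section 9.1.2:
- Suction: "Record volume of fluid in suction container (i.e. stomach juices and blood) prior to stomach drainage and again after". These readings are tied to stomach drainage, not to the start or end of adenoidectomy.
- Sponges: "Differential weight of any sponges applied to the tonsil bed to absorb blood". Only this component is specific to the tonsil bed.

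For operative time, the same section already uses a window that ends at the tonsillar bed: "time from the first incision to complete hemostasis".

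Section 13.4.1 lists the planned descriptive breakdowns: "blood loss will be reported for different age groups (ages 2-5 and ages 6-12) as well as for different sites, surgeons, and countries". Adenoidectomy is not among these breakdowns, nor among the data items listed in sections 9.1 and 9.1.2.

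**The concern.** The measurement window is anchored to the wrong operation. If the tonsils come out first, reading before the adenoidectomy gives what the study wants. If the adenoids come out first, a site has two options, and neither is sound as written:

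- **Follow the sentence.** The canister is read before any tonsil is cut, so the value is too low. This error favours success.
- **Set the sentence aside and read later.** Adenoid blood sits in the suction volume, and no baseline reading is specified to remove it. This error works against success.

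Mean blood loss against 31 mL is the sole hypothesis test and the stated success criterion (sections 5.2.1 and 13.4.1). Which error occurs, and how often, would follow site or surgeon habit. Because no listed data item records adenoidectomy or its order, the problem could not be reliably untangled after the fact.

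**Working it through.** **Inputs.** Goal 31 mL, expected mean 10 mL and SD 15.1 mL (section 13.4.1). N=60 and one-sided alpha 0.025 (section 13.2). The share f of affected cases and the volumes involved are not in the documents, so they are assumed below.

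**The plan's own figure.** The noncentrality is (31 − 10) × √60 / 15.1 = 10.77 with 59 degrees of freedom. The noncentral t distribution gives power of about 100%, so the stated power above 99% reproduces.

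**What counts as success.** The critical t is 2.001. At SD 15.1, the observed mean must be at or below 31 − 2.001 × 15.1/√60 = 31 − 3.90 = 27.1 mL. A mean merely under 31 mL is not enough.

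**Literal rule, affected cases recorded as 0 mL.** With true mean μ:
- observed mean m = (1 − f) × μ
- observed variance s² = (1 − f) × (15.1² + μ²) − m²
- cutoff = 31 − 2.001 × s/√60
- P(success) is the chance that the one-sample t-test rejects

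Worked case, μ = 35 and f = 0.20: m = 28.0. Then s² = 0.8 × (228.01 + 1225) − 784 = 378.4, so s = 19.5 and the cutoff is about 26.0 mL.

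| True mean | Share affected | Observed mean | SD | Cutoff | P(success) |
|---|---|---|---|---|---|
| 31 mL | 0% | 31.0 | 15.1 | 27.1 | 2.5% |
| 31 mL | 10% | 27.9 | 17.1 | 26.6 | about 28% |
| 31 mL | 20% | 24.8 | 18.3 | 26.3 | about 73% |
| 31 mL | 30% | 21.7 | 19.0 | 26.1 | about 96% |
| 35 mL | 10% | 31.5 | 17.8 | 26.4 | about 1% |
| 35 mL | 20% | 28.0 | 19.5 | 26.0 | about 21% |
| 35 mL | 30% | 24.5 | 20.4 | 25.7 | about 67% |
| 10 mL | 30% | 7.0 | 13.4 | 27.5 | about 100% |

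Simulation with normally distributed blood loss and the noncentral t approximation agree to within about one percentage point.

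**Rule set aside, adenoid blood included.** With the planned mean of 10 mL and extra volume b in a share f of cases, the mean is 10 + f × b and the variance is 15.1² + f(1 − f)b². Power is 99.98% with 10 mL added in every case, 99.6% with 20 mL in half, 75% with 20 mL in three quarters, and 57% with 30 mL in half.

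**The case against.** The strongest reply is that the sentence is itself a safeguard. In a tonsillectomy study, a surgeon told to measure before adenoidectomy would naturally finish the tonsils, measure, and then do the adenoids. That is probably what the sponsor meant. But the text does not say so, and an instruction that works only under an unstated order needs the order stated or the window re-anchored.

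A reader might infer that the value is wrong in every adenoidectomy-first case. The documents do not support that. The sponge weights are specific to the tonsil bed, and a site that zeroed or changed the canister unprompted could still obtain a correct figure.

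A reader might also treat any biased mean under 31 mL as a false success. It is not: a true mean of 35 mL with 20% zeros gives 28 mL, which is above the cutoff, and the test succeeds only about 21% of the time.

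The by-site and by-surgeon summaries and the between-site ANOVA in section 13.8 give partial protection. They could show a difference, but could not attribute it to operative order, and they would miss a bias shared by the sites.

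Finally, the eCRF and the separate SAP cited in section 13.8 are not in the supplied text. The supportable statement is that adenoidectomy is not listed in the protocol, not that it goes uncollected.

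**Conclusion.** The point holds as a gap in the measurement instruction for the primary endpoint. It is minor in expected effect and cheap to close. Its size depends on an unknown share of adenoidectomy-first cases and on how sites would record them. Under the zero-recording assumption, the chance of success at a true mean equal to the goal grows from 2.5% to between 28% and 96% as the affected share goes from 10% to 30%. If true blood loss is near the planned 10 mL, recording zeros changes nothing and moderate contamination does little; only large adenoid volumes in many cases would cost power. The issue is therefore mainly whether the measurement is valid and interpretable.

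A reader might go further and say that hemorrhage, readmission, pain and analgesic use must be separated by adenoidectomy. Section 13.5 says only "Proportions of the following events will be reported for the study", and section 13.4.2 plans descriptive summaries without tests. No section states that adenoid surgery contributes to these outcomes, and splitting 60 children would give small cells. Such a split is an optional descriptive addition, not a correction the documents require.

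**What to change.** In section 9.1.2, replace the timing parenthetical with a window tied to the tonsils: blood loss from first tonsil incision to complete hemostasis of the tonsillar bed, the end point already used for operative time. If another procedure came first, zero or read the canister and sponges at the start of the window. Read them again before any procedure that follows. This works in either order, so no surgical order should be prescribed.

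Record adenoidectomy (yes/no, and order) on the eCRF if it is not already there, and add it to the descriptive blood-loss breakdown in section 13.4.1. Tables of post-operative outcomes by adenoidectomy are optional.

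N, alpha and power are unchanged. The cost is one extra canister reading in some cases, one eCRF field, and a protocol amendment with the review and site training described in section 15.6.

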#### 9.1.4. Assessment Instruments

#### 9.1.4.1. Wong Baker FACES Pain Scale

The Wong Baker FACES pain scale is an instrument validated for ages 3+ to measure pain, by selecting a number on an ordinal 0-10 scale ("0" being no pain and "10" being the worst pain ever). Subjects will receive at least eleven copies of the Wong-Baker FACES® Pain Rating scale (below). Prior to the subject receiving the scale, the subject ID will be written on each page. On post-operative days 1 through 7, Day 10 (+/-1 day), Day 14 (+/-1 day), and Day 28 (+/-1 day), subjects and/or LAR(s) will be instructed to indicate the subject's degree of pain at the same time each morning prior to taking any pain medication by marking and dating the appropriate face.

#### 9.1.4.2. FLACC Behavioral Pain Assessment Scale

The FLACC behavioral pain assessment scale is an instrument validated for use for children ages 2 months 7 years of age to measure pain. A parent or guardian will rate the child's behavior across five (5) domains (Face, Legs, Activity, Crying, and Consolability) on a scale of 0-2 ("0" being no pain behavior and "2" being the highest pain behavior). Subjects will receive at least eleven copies of the FLACC behavioral pain assessment scale. Prior to the subject receiving the scale, the subject ID will be written on each page. On post-operative days 1 through 7, Day 10 (+/-1 day), Day 14 (+/-1 day), and Day 28 (+/-1 day), parent(s)/ will be instructed to indicate the subject's degree of pain at the same time each morning prior to taking any pain medication by rating the child's behavior according to the scale's instructions.

#### 9.1.4.3. Post-Operative Patient Diary

The patient diary will be provided to the subject/subject's LAR. This diary will be used to record any adverse events, or medicines that have been taken relative to the tonsillectomy procedure. The diary will also be used to record return to normal eating and living activities.

#### 9.1.5. Return to Clinic: Day 28 (+7)

On post-operative day 28 (+7) (end of study) the subject will return to the clinic to return their Wong-Baker FACES® pain rating scale(s) or FLACC Behavioral Pain Assessment Sales(s) and the Patient diary. Post-operative day 28 (from section 9.1.3) and Return to Clinic can be combined if both are completed on day 28.

MDT17024BZP

Version 5.0 (18 MAR 2019)

Page 25 of 47

Medtronic

#### 9.2. Prior and Concomitant Medications

Provided that the medications do not conflict with study-related procedures, or are not indicative of an underlying condition that would constitute an eligibility criteria violation, they will follow the normal medication regimen as prescribed by their doctor when proceeding with study participation. No specific post-operative regimen will be required for this study. Medications, including medications for pain, will be recorded as concomitant medications

